1.1 Synopsis

Protocol Title: Phase I, Open-Label, Single-Sequence Study of the Effect of Multiple Doses of Carbamazepine on Single-Dose Evobrutinib Pharmacokinetics in Healthy Participants

Short Title: DDI Study of Evobrutinib and Carbamazepine

CCI

Objectives and Endpoints:

Objectives	Endpoints	Ref #
Primary		
To investigate the effect of multiple doses of carbamazepine on the PK of a single dose of evobrutinib in healthy participants	
Plasma evobrutinib: $AUC_{0-\infty}$Plasma evobrutinib: C_{max}	1
Secondary		
To assess the safety and tolerability of evobrutinib when administered together with carbamazepine in healthy participants	
Nature, occurrence, severity, and seriousness of TEAEsAbsolute values and changes in safety laboratory tests from time of first dose to end of study participationSingle 12-lead ECGs evaluated by Investigator from time of first dose to end of study participationVital signs assessed from time of first dose to end of study participation	2
To characterize the effect of carbamazepine on additional evobrutinib PK parameters in healthy participants	
Plasma evobrutinib: CL/FPlasma evobrutinib: V_z/FPlasma evobrutinib: $AUC_{0-t_{last}}$Plasma evobrutinib: t_{max}Plasma evobrutinib: $t_{1/2}$	3
To characterize the effect of carbamazepine on evobrutinib metabolite (MSC2729909A) PK in healthy participants	
Plasma MSC2729909A: $AUC_{0-\infty}$Plasma MSC2729909A: $AUC_{0-t_{last}}$Plasma MSC2729909A: C_{max}Plasma MSC2729909A: t_{max}Plasma MSC2729909A: t_{lag}	4

Objectives	Endpoints	Ref #
	
 Plasma MSC2729909A: $t_{1/2}$ Plasma MSC2729909A: respective metabolic ratios M/P(AUC_{0-∞}) and M/P(C_{max}) 	

AUC=area under the concentration-time curve; C_{max}=maximum observed concentration; CL/F=apparent total body clearance; MR=metabolic ratio; M=metabolite; P=parent; PK=pharmacokinetics; t_{1/2}=apparent terminal half-life; t_{lag}=time prior to the first measurable (nonzero) concentration; t_{max}=time to reach the maximum observed concentration; Vz/F=apparent volume of distribution.

Overall Design: This will be a nonrandomized, open-label, single-sequence Phase I study in 18 healthy participants.

Brief Summary:

The purpose of this study is to investigate the effect of multiple doses of carbamazepine on single dose evobrutinib PK in healthy participants. Study details include:

[figure not shown]
- Study Duration: up to 54 days.
- Treatment Duration: 25 days.
- Visit Frequency: Participants will be resident in the Clinical Research Unit from Day -1 to Day 20 and return on Day 26 for a Safety Follow-Up visit.

CCI

Study Intervention Groups and Duration: Single-sequence study, 25 days

Involvement of Special Committee(s): No

1.2 Schema

1.3 Schedule of Activities

Assessments & Procedures	Screening													Safety Follow-Up	Notes	
Study Day	-28 to -2	-1	1	2	3	4	5	6 to 17	18	19	20	21	22	23 to 25	26	
Informed consent	X														Prior to any screening activity.	
Participants resident at CRU		X	X	X	X	X	X		X	X	X	X			X	
Eligibility criteria	X	X														Recheck of eligibility criteria on Day -1, (Sections 5.1 and 5.2).
Demography, height & weight	X															Demography to include, at minimum age (year of birth), sex, race, and ethnicity.
Medical history	X															
Physical examination	X	X													X	Brief examination on Day -1 Section 8.2.1.
FSH	X															In postmenopausal women.
Viral serology, TSH, QuantiFERON® test	X															
Clinical laboratory tests (blood and urine)	X	X						X ^a	X						X	a Safety lab to be collected from Day 10 to Day 14. Appendix 5 and Section 8.2.4.
Cotinine, drug screen, alcohol breath test, SARS-CoV-2	X	X														Appendix 5.
Safety ECG & vital signs	X	X	X	X					X	X	X				X	Predose, 4 and 6 hours postdose on Days 1 and 19. Sections 8.2.2 and 8.2.3.
AE/concomitant medication review	X	X	X	X	X	X	X	X	X	X	X	X	X	X		Section 6.8.
CCI																

Assessments & Procedures	Screening														Safety Follow-Up	Notes
Study Day	-28 to -2	-1	1	2	3	4	5	6 to 17	18	19	20	21	22	23 to 25	26	
Carbamazepine administration, mg				2x 100	2x 100	2x 200	2x 200	2x 300	2x 300	2x 300	2x 200 ^b	2x 200 ^b	2x 200 ^b	2x 100 ^b		First dosing on Day 2 after 24-hour PK sampling for evobrutinib. ^b On Day 20 evening dose, as well as on Days 21 to 25, participants will take carbamazepine at home. Twice daily administration (2x). Section 5.3.1, Section 6.1.
CCI									C C I	C C I					C C I	
Evobrutinib administration			X							X						Section 5.3.1, Section 6.1.
Evobrutinib and metabolite PK blood sampling			X	X						X	X					Sampling Days 1/2 and 19/20: Predose and 0.25, 0.5, 1, 1.5, 2, 2.5, 3, 4, 6, 8, 12, 16 and 24 hours postdose. Section 8.4.

CRU=clinical research unit; ECG=electrocardiogram; FSH=follicle stimulating hormone; PK=pharmacokinetics; SARS-CoV-2=severe acute respiratory syndrome coronavirus 2; TSH=thyroid stimulating hormone.

2 Introduction

Evobrutinib is an oral, selective, irreversible inhibitor of BTK which is in clinical development for the treatment of autoimmune diseases, including RMS.

Detailed information on the chemistry, pharmacology, efficacy, and safety of evobrutinib is in the IB.

There is extensive clinical experience in the use of carbamazepine. Complete information about the potential side effects of carbamazepine administration is described in the currently approved SmPC for carbamazepine.

CCI [REDACTED]

[REDACTED]

[REDACTED]

[REDACTED]

2.2 Background

Evobrutinib

Evobrutinib (also known as M2951 and MSC2364447C) is an oral, selective, irreversible inhibitor of BTK. Evobrutinib inhibits primary B cell responses, such as proliferation and antibody and cytokine release, without directly affecting T cells. Indirect effects on T cells can be mediated by BTK inhibition by blocking the B cell antigen presentation function. In addition, BTK inhibition blocks the activation of innate immune cells by immune complexes downstream of Fc receptor activation. All 3 mechanisms may play a role in the pathogenesis of various autoimmune diseases. Thus, BTK inhibition could provide clinical benefit in the treatment of multiple autoimmune diseases including RMS.

In clinical studies with healthy participants, evobrutinib was rapidly absorbed with a t_{max} of 0.5 to 1.5 hours under fasted conditions. Evobrutinib demonstrated dose-proportional PK (i.e., C_{max} and $AUC_{0-\infty}$) over the evaluated dose range of 25 to 500 mg single dose and 25 to 200 mg once daily multiple dose. Median $t_{1/2}$ was approximately 2 hours (range 1.8 to 2.6 hours) at relevant plasma concentrations following a single oral dose of 25 to 200 mg. Accumulation of evobrutinib is minimal with daily dosing (refer to IB).

Evobrutinib will be dosed under fed conditions in this study. Administration of evobrutinib utilizing the current TF2 formulation demonstrated that administration of evobrutinib TF2 30 minutes after the start of a high-fat breakfast resulted in 61% and 12% increases in AUC and C_{max} , respectively, relative to fasted conditions (Study MS200527_0077). Median (range) t_{max} under fed conditions was 1.5 hours (0.5 to 3 hours).

Carbamazepine

Carbamazepine (5H-dibenzo[b,f]azepine-5-carboxamide) has been in therapeutic use since 1962 ([Moshé 2009](#)). It is an essential medicine (WHO model list of essential medicines: 21st list, 2019) for the treatment of epilepsy, paroxysmal pain of trigeminal neuralgia, as well as for the prophylaxis of manic-depressive psychosis in patients unresponsive to lithium therapy (carbamazepine SmPC).

Carbamazepine is classified as a BCS Class II compound according to the FDA BCS guidance. Ingestion of food has no significant influence on the rate and extent of absorption. Carbamazepine is metabolized in the liver to an active epoxy-metabolite, primarily by CYP3A4. It induces CYP3A4 and CYP1A2 and thereby induces its own metabolism during prolonged treatment, which is complete in 3 to 5 weeks with a fixed dosing regimen. Physiologically based PK simulations indicated that 14 days are sufficient to reach the maximal effect on induction at 600 mg/day ([Xu 2011](#)). The elimination half-life of carbamazepine averages approximately 36 hours following a single oral dose, whereas after repeated administration it averages 16 hours to 24 hours (due to auto-induction), depending on the duration of the treatment ([Carbamazepine SmPC](#)).

2.3 Benefit/Risk Assessment

Evobrutinib

As of 31 July 2021, approximately 2,041 adult participants in 16 completed and 5 ongoing clinical studies have been exposed to evobrutinib, including healthy participants (243), participants with RMS (943), systemic lupus erythematosus (437), or rheumatoid arthritis (363), and participants with renal impairment (31) and hepatic impairment (24). Evobrutinib was generally safe and well tolerated in all participants. The TEAEs have been primarily mild to moderate in severity.

Evobrutinib treatment will be administered as a single dose of 45 mg each on Day 1 and Day 19 of this study under fed conditions. This regimen was previously tested in healthy participant studies and does not exceed exposures reached in first-in-human clinical Study EMR200527_001, where single doses of evobrutinib from 25 up to 500 mg and 14 days of dosing with 25, 75, and 200 mg/day were tested and shown to be well tolerated.

More detailed information about the known and expected benefits and risks and reasonably expected adverse events of evobrutinib may be found in the IB.

Based on the available nonclinical and clinical data to date, the conduct of the study, as specified in this protocol, is considered justifiable.

Carbamazepine

Carbamazepine will be dosed twice daily under fed conditions for 18.5 days at the CRU (from Day 2 morning dose to Day 20 morning dose; Section 6.1), followed by 5.5 days of tapering the dose down at home (starting from Day 20 evening dose to Day 25 evening dose). The gradual dose increase will be applied with 600 mg daily dose of carbamazepine administered from Day 6 onwards. Starting on Day 20, the dose will be tapered down over 6 days (Section 6.1). Maximum recommended dose for adults is 1,200 mg per day.

More detailed information about the known and expected benefits and risks and reasonably expected AEs of carbamazepine may be found in the [SmPC](#).

2.3.1 Risk Assessment

Safety Risks Applicable to Healthy Participants

Identified and Potential Risks of Clinical Significance	Summary of Data/Rationale for Risk	Mitigation Strategy
Evobrutinib		
Important identified risk: Elevated liver transaminases	Elevated liver transaminases have been observed in participants treated with evobrutinib across the program and is considered an important identified risk (for details see current IB Section 6.1). Elevations of liver transaminases (ALT, AST) were frequent, asymptomatic, and reversible, and occurred within 6 months of treatment. This has not been observed in healthy participants after a single dose nor in participants receiving short treatment with evobrutinib.	Participants with known history of hepatic disorder will not be included in the study. Study participants will be confined, and liver tests (e.g., ALT, AST) will be adequately monitored during the study.
Important potential risk: Embryo-fetal toxicity	Based on nonclinical findings, embryo-fetal toxicity is considered as an important potential risk in women of childbearing potential exposed to evobrutinib.	Only women of nonchildbearing potential are included in this study.
Carbamazepine (SmPC)		
Hepatitis, hepatic failure, vanishing bile duct syndrome	Hepatitis and vanishing bile duct syndrome (see also the hypersensitivity reactions below) are listed with rare frequency, while hepatic failure is considered very rare. Due to enzyme induction, some liver function tests in patients receiving carbamazepine may be found to be abnormal: particularly GGT and modest elevations in ALP.	The risk from potential overlapping toxicities with regards to liver function tests is considered as managed by adequate measurements such as eligibility criteria (Sections 5.1 and 5.2) and adequate monitoring. Inclusion will be only allowed for participants with adequate hepatic function.

Identified and Potential Risks of Clinical Significance	Summary of Data/Rationale for Risk	Mitigation Strategy
Severe cutaneous adverse reactions including SJS, TEN (also known as Lyell's syndrome), and acute generalized exanthematous pustulosis, urticaria	
Serious TEN and SJS have been reported very rarely with carbamazepine. Patients with serious dermatological reactions may require hospitalization, as these conditions may be life-threatening and may be fatal. Most of the SJS/TEN cases appear in the first few months of treatment with carbamazepine. These reactions are estimated to occur in 1 to 6 per 10,000 new users in countries with mainly Caucasian populations.
 
Mild skin reactions e.g., isolated macular or maculopapular exanthema, can also occur and are mostly transient and not hazardous, however, it may be difficult to differentiate the early signs of more serious skin reactions from mild transient reactions, and consideration must be given to immediately withdraw the drug should the reaction worsen with continued use.
	The risk is considered as managed by adequate measurements such as eligibility criteria (Sections 5.1 and 5.2) and by close monitoring for skin reactions.
Hypersensitivity reactions including DRESS	
DRESS, a delayed multi-organ hypersensitivity disorder with fever, rash, vasculitis, lymphadenopathy, pseudo lymphoma, arthralgia, leukopenia, eosinophilia, hepato-splenomegaly, abnormal liver function tests and vanishing bile duct syndrome, which may occur in various combinations. Other organs may also be affected (e.g.; lungs, kidneys, pancreas, myocardium, colon).
 
In general, if signs and symptoms suggestive of hypersensitivity reactions occur, carbamazepine should be withdrawn immediately.
 
Patients who have exhibited hypersensitivity reactions to carbamazepine should be informed that 25% to 30% of these patients may experience hypersensitivity reactions with oxcarbazepine (Trileptal). Cross-hypersensitivity can occur between carbamazepine and aromatic antiepileptic drugs (e.g., phenytoin, primidone, and phenobarbital).
	The risk is considered as managed by adequate measurements such as eligibility criteria (Sections 5.1 and 5.2) and by close monitoring of skin reactions, fever and lymphadenopathy (physical examination).
Agranulocytosis, aplastic anemia, pancytopenia, leucopenia, thrombocytopenia, eosinophilia	Very rare agranulocytosis and aplastic anemia have been associated with carbamazepine; however, due to the very low incidence of these conditions, meaningful risk estimates for carbamazepine are difficult to obtain. Decreased platelet or white blood cell counts occur rarely to very commonly.	The risk is considered as managed by adequate measurements such as eligibility criteria (Sections 5.1 and 5.2) and by monitoring of hematology parameters and early toxic signs and symptoms such as fever, sore throat, rash, ulcers in the mouth, easy bruising, and petechial or purpuric hemorrhage.
Ataxia, dizziness, somnolence, diplopia, fatigue, accommodation disorders (e.g., blurred vision)	Events may lead to falls and, consequently fractures or other injuries.	The risk is considered as managed by adequate measures such as eligibility criteria (Sections 5.1 and 5.2), confinement during the study, and advising participants to be careful when operating machinery during the outpatient tapering-down period.

Identified and Potential Risks of Clinical Significance	Summary of Data/Rationale for Risk	Mitigation Strategy
Study Procedures		
Blood draw	Blood draws have the potential to cause AEs such as fainting or hematoma.	Amount of blood drawn will be strictly controlled. Participants will be in a hospital setting with support from highly trained professionals.
ECG	Contact allergies can develop during ECG procedures.	Participants with known contact allergies will not be included in the study.
Other		
Not applicable		

AE=adverse event; ALP=alkaline phosphatase; ALT=alanine aminotransferase; AST=aspartate aminotransferase; DRESS=drug reaction with eosinophilia and systemic symptoms; ECG=electrocardiogram; GGT=Gamma-glutamyl transferase; IB=investigator brochure; SJS=Stevens-Johnson syndrome; SmPC=summary of product characteristics; TEN=toxic epidermal necrolysis.

Safety Risks not Applicable for Healthy Participants

Identified and Potential Risks of Clinical Significance	Summary of Data/Rationale for Risk	Mitigation Strategy
Carbamazepine (SmPC)		
Renal damage, hyponatremia	In patients with preexisting renal conditions associated with low sodium or in patients treated concomitantly with sodium-lowering medicinal products.	Not expected to constitute the risk for healthy participants. The risk is considered as managed by adequate measures such as exclusion criteria (Section 5.2).
Hypothyroidism	Serum concentrations of thyroid hormones may be reduced due to enzyme induction requiring an increase in dose of thyroid replacement therapy in patients with hypothyroidism.	Not expected to constitute the risk for healthy participants. The risk is considered as managed by adequate measures such as exclusion criteria (Section 5.2).
Suicidal behavior /ideation	Suicidal ideation and behavior have been reported in patients treated with antiepileptic agents in several indications (note the indications for carbamazepine can be considered as the risk). The mechanism of this risk is not known, and the available data do not exclude the possibility of an increased risk for carbamazepine.	Not expected to constitute the risk for healthy participants. The risk is considered as managed by adequate measures such as exclusion criteria (Section 5.2).
Cardiovascular disorders including conduction disorders, arrhythmia and atrioventricular block with syncope	Tachycardia, atrioventricular block, premature ventricular contractions, ventricular tachycardia and junctional escape rhythms have been reported in patients due to carbamazepine toxicity.	The risk is considered as managed by adequate measurements such as eligibility criteria (Sections 5.1 and 5.2) and scheduled monitoring of ECG.

ECG=electrocardiogram; SmPC=summary of product characteristics.

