8.2.1 Physical Examinations

- A complete physical examination will include, at a minimum, assessments of the skin, cardiovascular, respiratory, gastrointestinal and neurological systems, and abdomen (liver and spleen).
- A brief physical examination will include, at a minimum, assessments of the skin, lungs, cardiovascular system, and abdomen (liver and spleen).
- Investigators will pay special attention to clinical signs related to previous serious illnesses.

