8.2.2 Vital Signs

- Blood pressure and participant's position; pulse; respiratory rate; tympanic temperature and location of measurement, weight, and height (at Baseline only) will be measured and recorded.
- Blood pressure and pulse measurements will be preceded by at least 5 minutes of rest for the participant in a quiet setting without distractions (e.g., television, cell phones) and measured with an automated device. Manual techniques will be used only if an automated device is not available.

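### The protocol names physical examination as the monitoring for carbamazepine hypersensitivity, but schedules no examination on any of the 24 carbamazepine days and no temperature on Days 3 to 17 or 21 to 25

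*Protocol*

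**What the plan says.** **The stated mitigation.** In the risk table of protocol Section 2.3.1, the row on hypersensitivity reactions including DRESS gives two safeguards: the eligibility criteria, and management "by close monitoring of skin reactions, fever and lymphadenopathy (physical examination"). Physical examination is thus named as the means. Two neighbouring rows rely on related observation without naming a method. Severe cutaneous reactions are to be managed "by close monitoring for skin reactions", and blood disorders "by monitoring of hematology parameters and early toxic signs and symptoms such as fever, sore throat, rash" and similar signs.

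**The schedule.** In Section 1.3 the physical examination row has three marks: Screening, Day -1 and Day 26. Its note reads "Brief examination on Day -1 Section 8.2.1". Safety ECG and vital signs share one row, marked at Screening and on Days -1, 1, 2, 18, 19, 20 and 26. Section 8.2.2 places "tympanic temperature and location of measurement" among the vital signs, so scheduled fever checks follow that row.

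**The content of the examination.** Section 8.2.1 states: "A brief physical examination will include, at a minimum, assessments of the skin, lungs, cardiovascular system, and abdomen (liver and spleen"). The complete examination adds the neurological and gastrointestinal systems. Neither minimum list names lymph nodes.

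**The dosing period.** Section 6.1 gives carbamazepine twice daily on Days 2 to 25, and Section 2.3 places the doses from the evening of Day 20 onward at home.

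**The concern.** The risk table tells an ethics committee how a serious risk to healthy volunteers, who receive no benefit, is being controlled. For hypersensitivity it points to an examination. Set against the schedule, that examination takes place before carbamazepine starts and again after it has ended, but not while it is being taken.

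This matters because Section 2.3.1 itself says that early signs of serious skin reactions can be hard to tell from mild ones, and that suspected hypersensitivity calls for prompt withdrawal of carbamazepine. Both depend on signs being found. A low fever or enlarged nodes that the participant does not mention and staff do not notice would meet no scheduled check between Day 3 and Day 17, and none during the home taper.

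**Working it through.** No sample-size or power formula applies. The check is a day count from Sections 1.3 and 6.1.

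**Reproducing the protocol's own figure.** Section 2.3 gives 18.5 carbamazepine days in the unit and 5.5 at home. Days 2 to 19 are 18 days, plus the Day 20 morning dose (0.5) = 18.5. The Day 20 evening dose (0.5) plus Days 21 to 25 (5) = 5.5. Total: 18.5 + 5.5 = 24 days, which agrees with Days 2 to 25 in Section 6.1.

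**Scheduled checks by dose level** (doses by day from Section 6.1, marks from Section 1.3):

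| Days | Carbamazepine per day | Number of days | Days with examination | Days with vital signs and temperature |
|---|---|---|---|---|
| 2–3 | 200 mg | 2 | 0 | 1 (Day 2) |
| 4–5 | 400 mg | 2 | 0 | 0 |
| 6–19 | 600 mg | 14 | 0 | 2 (Days 18, 19) |
| 20–22 | 400 mg | 3 | 0 | 1 (Day 20) |
| 23–25 | 200 mg | 3 | 0 | 0 |
| Total | | 24 | 0 | 4 |

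**Results**
- Carbamazepine days with a scheduled examination: 0 of 24.
- Carbamazepine days without scheduled temperature: 24 − 4 = 20. These are Days 3 to 17 (15 days) and Days 21 to 25 (5 days).
- Both increases (Day 4 and Day 6) fall inside the Day 3 to 17 gap.
- Days at 600 mg/day without scheduled temperature: 14 − 2 = 12, and 12/14 = 86%.

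**What is scheduled in the gap.** Adverse event and medication review is marked on every carbamazepine day. One safety laboratory draw falls between Days 10 and 14, followed by another on Day 18.

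**Is this a table-reading artefact?** Some rows of Section 1.3 are displaced in the extracted text; the residence row is one. The evobrutinib, carbamazepine and PK sampling rows line up with their own notes, and the examination and vital-signs rows are consistent with theirs. The examination row has only three marks, two of which are Screening and Day -1. Under any alignment, at most one can fall after dosing starts.

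**Day 2.** The schedule gives no clock time for the Day 2 vital signs, and carbamazepine starts that day only after the 24-hour PK sample. The count of 4 therefore gives the plan the benefit of the doubt.

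**The case against.** The strongest reply is that Section 2.3.1 sets no frequency, and that participants are far from unobserved. Eligibility criteria come first among the safeguards: Section 5.2 excludes HLA-B*1502 and HLA-A*3101 carriers and relevant drug hypersensitivity, and Appendix 5 includes the HLA tests. Participants live in the unit until Day 20, and Section 2.3.3 gives ongoing observation as the reason. Adverse events are reviewed daily, and Section 8.2 has investigators record what they see as well as what they are told. The laboratory draws cover eosinophils, white cells and liver enzymes, all listed among DRESS features. Additional tests are allowed at any time, and unscheduled examinations are not barred. All of this stands as partial mitigation. It does not supply the examination that the hypersensitivity row names: laboratory tests do not examine skin or nodes, and no temperature check is attached to residence or to the daily review.

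A reader might infer more than the documents support:

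- *That the ECG commitment is also broken.* It is not. Section 2.3.1 promises only "scheduled monitoring of ECG". ECGs are marked on carbamazepine Days 2, 18, 19 and 20, with Days 18 and 19 at 600 mg/day. That risk row also sits in the table of risks not applicable to healthy participants.
- *That hypersensitivity goes unmonitored from Day 3 to Day 17, or that a reaction could first be detected on Day 18.* That holds only for scheduled temperature, not for an observed rash or a laboratory sign.
- *That the benefit/risk conclusion rests on absent safeguards.* Section 2.3.3 cites exclusion criteria, laboratory monitoring, vital signs, ECGs and residence. Only part of its support is thin.
- *That lymph nodes will not be examined even on Day 26.* The lists in Section 8.2.1 are minimums. The text supports only that nodes are not required.
- *That the secondary safety endpoints are undermined.* The objective concerns evobrutinib given with carbamazepine. Measurements on Days 1 to 2 and 18 to 20 bracket both evobrutinib doses, with the detailed times "Predose, 4 and 6 hours postdose on Days 1 and 19".

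**Conclusion.** The mismatch is real and limited in scope. For hypersensitivity, Section 2.3.1 relies on physical examination of skin, fever and lymph nodes, and Section 1.3 provides that examination on none of the 24 carbamazepine days. Temperature is scheduled on 4 of the 24, with an unbroken 15-day gap over both dose increases, and Section 8.2.1 does not require the nodes to be examined. The point concerns what is scheduled, not what staff may do on their own initiative. It rests on the extracted schedule marks being correctly placed, on Section 6.1 for the doses by day, and on vital signs being the only scheduled source of temperature. It is worth correcting because it bears on safety and costs little, but it does not show that participants are unprotected or that the trial's endpoints are at risk.

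**What to change.** Reconcile Sections 1.3, 2.3.1 and 8.2.1 by one of two routes.

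1. **Deliver the stated monitoring.** Add lymph nodes to the minimum content of the brief and complete examinations in Section 8.2.1. In Section 1.3, mark the brief examination with temperature that Section 2.3.1 relies on during the resident carbamazepine period, on days the sponsor chooses.
2. **Correct the statement.** Reword the Section 2.3.1 mitigation and the Section 2.3.3 conclusion so that they describe only the monitoring actually scheduled, and let the risk be judged on that basis.

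The first route needs a protocol amendment, a few minutes of on-site staff time for each of the 18 planned participants, and slightly more data entry. The second costs only an amendment of the text. Neither changes a dose, a stopping rule or the ECG schedule.
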